**Table 3. Schedule of Activities for Patients Receiving Non-Intensive Chemotherapy: Glasdegib/Placebo + Azacitidine**

	Screening	Treatment							Post Treatment		
		Cycle 1 (28 –day cycle) (-3/+3 day time window)			All subsequent cycles (28 –day cycles) (-3/+3 day time window)	HSCT Period 			End of Treatment Visit 	Post Treatment Follow-Up Visits (±7 days) 	Long-Term Follow-Up Activity Log (±14 days) 
Protocol Activity	(≤28 days prior to study entry)	Day 1	Day 7 (±3 days)	Day 15 (±3 days)	Day 1 (-3/+28 days)	First day of conditioning	HSCT Day 0	> Day 0, monthly (±2 days)	(Within 14 days after last dose)		
Other Clinical Assessments											
Serious and non-serious Adverse Event Monitoring 	X	Continuous monitoring; except during HSCT period							X 	X 	X 
Review Prior/Concomitant Treatments 	X	Continuous Monitoring; except during HSCT period							X		
Recording of Red Blood Cell and Platelet Transfusions 	X	Continuous Monitoring except during HSCT period							X		
Patient Reported Outcomes 		X	X	X	X	X	X	X	X	X	X
Pharmacokinetic Sampling											
Blood samples for Glasdegib PK 	Refer to Table 4 Pharmacokinetics & ECG Schedule for Patients Receiving Non-Intensive Chemotherapy: Glasdegib/Placebo + Azacitidine										
CCI											

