32. **HSCT related information:** Donor details, type of transplant, day of donor stem cell infusion, and conditioning regimen (including radiation) will be collected in the CRF. Presence of GVHD prior to resuming glasdegib/placebo post HSCT will be reported in the CRF. HSCT-related information must be made available to the B1371019 study and must be able to be monitored. Post Remission HSCT period (HSCT period) is defined as time from start of conditioning until resuming glasdegib/placebo, death, withdrawal of consent, or entering follow up period post HSCT. No concomitant medications (including transfusions) will be collected during the HSCT period. Day 0 is defined as the day of stem cell infusion (HSCT). See Section 7.1.8.
33. **ANC engraftment:** ANC engraftment is defined as  $\geq 0.5 \times 10^9/L$  for 3 consecutive days without growth factor support. ANC engraftment must be documented prior to continuing glasdegib or placebo post HSCT.
34. **SAE Collection post remission HSCT Period from HSCT (Day 0) until resumption of study therapy, death, or withdrawal:** All deaths regardless of causality, Grade 3 and Grade 4 treatment related AEs, and SAE events that the investigator believes have at least a reasonable possibility of being related to study drug during the HSCT period are to be reported to the sponsor. Once subjects resume glasdegib or placebo following HSCT, events summarized in Table 13 will be reported.

35. **Interrupt glasdegib/placebo at least 28 days prior to day of hematopoietic stem cell infusion (HSCT).** Following HSCT, subjects may continue glasdegib or matching placebo 30 -60 days post first day of HSCT, once there is ANC engraftment, no ongoing  $\geq$  Grade 2 GVHD, and no ongoing SAEs that prevent resuming glasdegib or placebo, in the judgement of the investigator. Patients may continue on glasdegib treatment following HSCT or up to 2 years post randomization or until CR MRD-negative disease is confirmed at 2 consecutive time points post HSCT, whichever comes first. The 2 consecutive time points will be done as part of the scheduled marrow assessments.

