#### **Non-Intensive Chemotherapy Study:**

Subjects will be stratified at randomization by genetic risk (favorable vs intermediate vs adverse by ELN genetic risk categories) and age ( $<75$  years vs  $\geq 75$  years).

A total of 320 subjects who are not candidates to receive Intensive Chemotherapy will receive treatment as follows:

- Experimental Therapy: Glasdegib 100 mg PO QD or matching placebo is to be administered by mouth daily beginning on Day 1 of chemotherapy and will continue if subjects demonstrate reasonable evidence of clinical benefit and do not meet the criteria for progression regardless of any delays/modifications in the chemotherapy treatment. Subjects will continue glasdegib or placebo until disease progression, unacceptable toxicity, consent withdrawal, or death, whichever comes first.
- Azacitidine will be administered by subcutaneous injection (SC) or intravenous (IV) infusion daily for 7 days, in 28 day cycles for as long as they do not meet the criteria for disease progression, unacceptable toxicity, consent withdrawal, or death, whichever comes first.
- Alternate dosing schedules to administer the 7 doses of azacitidine to accommodate patient and treatment center availability is allowed. Dose adjustments will be made according to local approved label for azacitidine. In addition, each subsequent cycle may be delayed for up to 28 days to allow for recovery of blood counts. Patients should continue to receive treatment as long as they do not meet the criteria for progression.
- Per Investigator discretion, HSCT may be performed. Glasdegib or placebo will be interrupted at least 28 days before HSCT Day 0 (day of stem cell infusion), and resumed 30-60 days post HSCT after documentation of ANC engraftment ( $\geq 0.5 \times 10^9/L$  for 3 consecutive days without growth factor support), no ongoing  $\geq$  Grade 2 GVHD, and no ongoing SAEs that prevent resumption of glasdegib/placebo in the judgement of the Investigator. If therapy is resumed, glasdegib/placebo may continue up until 2 consecutive CR MRD-negative results, death or consent withdrawal.
- For patients undergoing HSCT, azacitidine may continue prior to HSCT, per the investigator discretion. Following HSCT, azacitidine will not be resumed.

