**Table 13. Adverse Event Reporting**

Safety Event	Recorded on the CRF	Reported on the CT SAE Report Form to Pfizer Safety Within 24 Hours of Awareness
SAE	All	All
HSCT Day 0 until resume study therapy, death, withdrawal or post-treatment follow up: All deaths, Grade 3/Grade 4 treatment-related AEs, and treatment related SAEs	Related to glasdegib or placebo and deaths regardless of causality a	Serious and related to glasdegib or placebo and deaths regardless of causality
Non-serious AE	All	None
Exposure to the investigational product under study during pregnancy or breastfeeding, and occupational exposure	All (regardless of whether associated with an AE), except occupational exposure	Exposure during pregnancy, exposure via breastfeeding, occupational exposure (regardless of whether associated with an AE)
Note: Serious adverse events occurring to a patient after the active reporting period has ended should be reported to the sponsor if the investigator becomes aware of them; at a minimum, all serious adverse events that the investigator believes have at least a reasonable possibility of being related to study drug are to be reported to the sponsor. a. In Germany only: All SAEs, regardless of causality, will be recorded on the CRF.		

All observed or volunteered events regardless of treatment group or suspected causal relationship to the investigational product(s) will be reported as described in the following paragraphs.

Subjects must be followed for AEs for 28 days after the last treatment administration or until all drug-related toxicities have resolved, whichever is later; or earlier than 28 days should the patient commence another anticancer therapy in the meantime. For serious adverse events (SAEs), the active reporting period to Pfizer or its designated representative begins from the time that the patient provides informed consent, which is obtained prior to the patient's participation in the study, (ie, prior to undergoing any study related procedure and/or receiving investigational product), through and including 28 calendar days after the last administration of the investigational product. Serious adverse events occurring to a patient after the active reporting period has ended should be reported to the sponsor if the investigator becomes aware of them; at a minimum, all serious adverse events that the investigator believes have at least a reasonable possibility of being related to study drug are to be reported to the sponsor.

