- The HSCT Post Remission Period (HSCT Period) is defined as time from the start of the conditioning regimen until the subject restarts glasdegib or placebo, death, post study follow up, or withdrawal. For subjects being treated with HSCT, subjects must be followed for AEs for at least 28 days after the last investigational treatment administration prior to HSCT. Following HSCT Day 0, all deaths regardless of causality, Grade 3/Grade 4 treatment-related AEs, and SAE events that the investigator believes have at least a reasonable possibility of being related to study drug during the HSCT period are to be reported to the sponsor. In Germany only: All SAEs, regardless of causality, will be recorded on the CRF.

- Once subjects resume glasdegib or placebo following HSCT, events summarized in [Table 13](#) will be reported.

Events listed in the table above that require reporting to Pfizer Safety on the CT SAE Report Form within 24 hours of awareness of the event by the investigator **are to be reported regardless of whether the event is determined by the investigator to be related to an investigational product under study**. In particular, if the SAE is fatal or life-threatening, notification to Pfizer Safety must be made immediately, irrespective of the extent of available event information. This time frame also applies to additional new (follow-up) information on previously forwarded reports. In the rare situation that the investigator does not become immediately aware of the occurrence of an event, the investigator must report the event within 24 hours after learning of it and document the time of his/her first awareness of the event.

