### 3.5. Safety Endpoints

Safety endpoints will be summarized based on the on-treatment period unless otherwise specified.

On-treatment is defined as the time from the first dose of study treatment to last dose prior to HSCT + 28 days and if applicable, from first dose post-HSCT to last dose + 28 days or start of new anti-cancer drug therapy (minus 1 day), whichever occurs first. Note that conditioning regimens for HSCT (regardless of whether glasdegib is resumed after HSCT) are not considered “new anti-cancer drug therapy”. Adverse events occurring on the same day as the first dose of study treatment will be considered to have occurred during the on-treatment period. All other assessments which occur on the same day as the first dose of study treatment will be considered baseline assessments (see [Section 3.4](#) for the definition of baseline).

Safety data collected outside the on-treatment period as described above will be listed but not summarized.

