#### **6.6.1. Adverse Events**

All analyses will be based on treatment emergent events unless otherwise specified. Treatment emergent is defined in [Section 3.5.1](#).

A high level summary of adverse events will include the number and percent of patients with:

- Any Adverse Event;
- Serious AE;
- Adverse Events with maximum CTCAE Grade 3-4;
- Grade 5 events;
- AEs leading to dose interruptions separately for each study drug, for chemotherapy, and for any study treatment;

- AEs leading to dose reductions separately for each study drug, for chemotherapy, and for any study treatment;
- AEs leading to withdrawal separately for each study drug, for chemotherapy, and for any study treatment.

Additionally, the number of events reported for each of the categories above will be provided. Each unique adverse event at the PT level in each treatment arm of the study for a patient is included in the count.

Seriousness, toxicity grade, action taken (interruption, reduction, and withdraw) are as reported by the investigator on the adverse event CRF.

Summaries by treatment arm, SOC and PT in decreasing frequency based on the frequencies observed in the glasdegib arm will be provided for:

- Treatment Emergent Events by Maximum Toxicity Grade (All Causality);
- Treatment Emergent Events by Maximum Toxicity Grade (Treatment Related);
- Serious Treatment Emergent Events by Maximum Toxicity Grade (All Causality);
- Serious Treatment Emergent Events by Maximum Toxicity Grade (Treatment Related).

An event will be considered treatment related if the investigator considered the event related to the study drug or this information is unknown.

The above four summaries will also be provided separately for (1) treatment emergent events prior to HSCT, (2) non-treatment emergent events during HSCT, and (3) treatment emergent events after HSCT.

The following summaries will be provided by treatment arm and PT (ie, summaries will not include SOC) in decreasing frequency based on the frequencies observed in the glasdegib arm for:

- Treatment Emergent Events (All Causality) Experienced by  $\geq 10\%$  of patients in either treatment arm;
- Treatment Emergent Events (All Causality) by Preferred Term and Maximum Toxicity Grade;
- Treatment Emergent Grade 3-5 Events (All Causality) by Preferred Term and Maximum Toxicity Grade;

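### AE/SAE collection rules around transplant can leave days with no active rule, contradict one another, and feed SAP tables labelled all-causality

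*Protocol*

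**What the plan says.** **Hold before transplant.** The Protocol Summary, Section 3 and Section 5.5.1.2 stop glasdegib/placebo at least 28 days before Day 0. This is a minimum; no maximum is given. Table 7 (intensive study) interrupts all study therapy. Table 8 (non-intensive study) interrupts only glasdegib/placebo, and Section 3 adds: "For patients undergoing HSCT, azacitidine may continue prior to HSCT, per the investigator discretion".

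**Collection rules, Protocol Section 8.1.** For transplanted subjects, "subjects must be followed for AEs for at least 28 days after the last investigational treatment administration prior to HSCT". The same bullet says that the HSCT period "is defined as time from the start of the conditioning regimen until the subject restarts glasdegib or placebo". The reduced set in Table 13, however, runs from "HSCT Day 0 until resume study therapy, death, withdrawal or post-treatment follow up". It covers all deaths, related Grade 3/4 AEs and related SAEs; in Germany all SAEs go on the CRF. Table 1 footnote 36 and Table 3 footnote 34 also start at Day 0.

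**Schedule for the non-intensive study.** The AE row of Table 3 reads "Continuous monitoring; except during HSCT period". Footnote 34 to that table nevertheless lists as reportable in the period "All deaths regardless of causality, Grade 3 and Grade 4 treatment related AEs, and SAE events that the investigator believes" may be related to study drug.

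**SAP.** Section 3.5: "On-treatment is defined as the time from the first dose of study treatment to last dose prior to HSCT + 28 days". Section 3.4 takes the last dose of any study drug. Section 6.6.1 repeats four AE summaries, two of them all-causality, for "2) non-treatment emergent events during HSCT".

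**The concern.** A site with a patient going to transplant needs one answer to the question of which events to record on a given day. The protocol gives none for some days before Day 0, and conflicting answers for others. Conditioning is where this bites: the protocol counts it as part of the HSCT period but starts the HSCT reporting rule after it.

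The overall safety profile is a secondary objective of both studies. If active AE/SAE collection lapses during conditioning, toxicity in that window enters the database unevenly across sites. Tables headed all-causality would then combine days of full, reduced and passive collection and would understate all-cause event rates. Events not recorded at the time may not be recoverable later.

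**Working it through.** The plan states no figure on this point, so the check is a count of days and a comparison of sections. Days use the protocol's numbering (infusion = Day 0; SAP 5.2.3 calls it Day 1).

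**1. Do the windows join?** Let H be the number of days from the last investigational dose to Day 0. Section 5 names glasdegib, azacitidine, daunorubicin and cytarabine as investigational products.

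- The 28-day follow-up ends, inclusive, on Day −(H − 28).
- The reduced rule starts on Day 0.
- Days under neither rule = max(0, H − 29).

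The documents give no conditioning length, so 4, 7 and 10 days ending on Day −1 are assumed.

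| H | Follow-up ends | Uncovered days | Of 4 conditioning days | Of 7 | Of 10 |
|---|---|---|---|---|---|
| 28 | Day 0 | 0 | 0 | 0 | 0 |
| 29 | Day −1 | 0 | 0 | 0 | 0 |
| 30 | Day −2 | 1 | 1 | 1 | 1 |
| 32 | Day −4 | 3 | 3 | 3 | 3 |
| 35 | Day −7 | 6 | 4 | 6 | 6 |
| 42 | Day −14 | 13 | 4 | 7 | 10 |
| 56 | Day −28 | 27 | 4 | 7 | 10 |

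Section 5.5.5.1 limits interruptions outside the HSCT period to 28 consecutive days. If that caps the hold before conditioning, then for conditioning of c days the longest hold is H = 28 + c. The uncovered days are then (28 + c) − 29 = c − 1, that is 3 of 4, 6 of 7 or 9 of 10. The cap does not close the gap.

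The early-stop clause in Section 8.1 is also unclear. AE follow-up may end before 28 days if another anticancer therapy starts, and the protocol does not say whether conditioning counts. SAP 3.5 says that it does not. A site that reads the protocol the other way would stop at conditioning even at H = 28.

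**2. Table 3.** Its AE row switches monitoring off for the whole HSCT period. Footnote 34 and Table 13 require reporting within it, and Section 5.5.1.3 sends the reader to Section 8 for the rule. The equivalent row of Table 1 avoids the conflict by pointing to footnotes 34 and 36.

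**3. Azacitidine close to transplant (non-intensive study).** Suppose the last azacitidine dose is on Day −10. Then −10 + 28 = Day +18. The Section 8.1 bullet requires AE follow-up to Day +18. SAP 3.5 treats those days as on-treatment, and SAP 5.2.3 describes collection as limited only after that point. Table 13 applies the reduced set from Day 0. Two rules therefore govern Day 0 to Day +18, which is 19 days inclusive.

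**4. SAP 6.6.1.** From Day 0, Table 13 admits events by relatedness to glasdegib/placebo, apart from deaths; Germany also records unrelated SAEs. An all-causality table for the period cannot be filled from those data. The treatment-related versions need a qualifier too, because non-serious related Grade 1–2 events are not in the reduced set. SAP 3.5 also says that safety data outside the on-treatment window are listed and not summarized, which fits poorly with ordering these summaries.

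**The case against.** Much can be said for the plan, and part of it stands.

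- **Deaths.** A reader might infer that deaths during conditioning escape collection. They do not. Section 6.4 follows survival in all subjects, and SAP 6.6.2 tabulates deaths on study, with primary reason, from the Notice of Death form.
- **Backstops.** Section 8.1.4.1 makes later SAEs of any cause reportable if the investigator learns of them. Section 7.1.8 requires AEs still ongoing after HSCT to be recorded, and Section 5.8 requires HSCT-related medical history for subjects who resume drug. Follow-up also continues until drug-related toxicity resolves. These stand, but the first is passive, and the others do not reach unrelated events that resolved before drug was resumed.
- **Section 8.1.4.** It has no HSCT exception, so for a subject who resumes drug it literally covers the interval. A site cannot know in advance who will resume. For subjects who die or never resume, the 28 days run from the dose before transplant.
- **Azacitidine overlap.** A reader might infer lost data. That is not established, because the Section 8.1 bullet and SAP 5.2.3 already call for full follow-up. It is a conflict with Table 13.
- **Table 3 and the SAP labels.** Both can be called slips. Few non-intensive transplants are expected, SAP 5.2.3 discloses limited data, the events are labelled non-treatment emergent, and treatment-related versions are also ordered. This lowers the stakes but leaves the wording wrong.
- **Equal rules.** Both blinded arms share the same collection rules, so nothing here points to a bias between arms.

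**Conclusion.** The concern holds in this form: the collection rules around HSCT do not join up and conflict in three further places.

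The gap is conditional. It is zero when the last investigational dose is 28 or 29 days before Day 0 and grows by one day for each further day of hold. Under the assumed regimen lengths it ranges from none of conditioning to all of it. What can be missed is active capture of conditioning toxicity that resolves or is judged unrelated, and of a conditioning death as an SAE.

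It is tempting to turn this into a count by applying a transplant rate to the 400 intensive subjects. The documents give neither a transplant rate nor a distribution of hold lengths, and a transplanted subject with a short hold has no gap, so no count is supported.

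The Table 3 contradiction and the mislabelled SAP summaries need no assumption. The azacitidine conflict arises only in the non-intensive study, when the last dose falls within 28 days of transplant. The primary OS analysis is unaffected. This should be corrected as a matter of safety data collection and reporting.

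**What to change.** 1. Reconcile the Section 8.1 bullet, Table 13, Table 1 footnote 36, Table 3 footnote 34 and Section 8.1.4 to one collection start point that leaves no uncovered day between the end of the 28-day window and the reduced rule. State which rule governs when the 28-day window runs past Day 0, and whether conditioning counts as another anticancer therapy for AE follow-up.
2. In the AE row of Table 3, replace the exception with a reference to footnote 34, following Table 1.
3. In SAP 6.6.1, label the HSCT-period tables by what was collected: deaths of any cause, treatment-related Grade 3/4 AEs and treatment-related SAEs. List unrelated German SAEs separately, and align SAP 3.5 with these summaries.

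None of this touches dosing, the length of the hold or transplant practice. The cost is wording in Section 8, two footnotes, one table cell and two SAP sections, plus a few more days of limited event reporting for some transplanted subjects.

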#### **8.1.1. Additional Details on Recording Adverse Events on the CRF**

All events detailed in the table above will be recorded on the AE page(s) of the CRF. It should be noted that the CT SAE Report Form for reporting of SAE information is not the same as the AE page of the CRF. When the same data are collected, the forms must be completed in a consistent manner. AEs should be recorded using concise medical terminology and the same AE term should be used on both the CRF and the CT SAE Report Form for reporting of SAE information.

#### **8.1.2. Eliciting Adverse Event Information**

The investigator is to record on the CRF all directly observed AEs and all AEs spontaneously reported by the subject. In addition, each study subject will be questioned about the occurrence of AEs in a non-leading manner.

### **8.1.3. Withdrawal from the Study Due to Adverse Events (see also the [Subject Withdrawal Section](#))**

Withdrawal due to AEs should be distinguished from withdrawal due to other causes, according to the definition of AE noted below, and recorded on the CRF.

When a subject withdraws from the study because of an SAE, the SAE must be recorded on the CRF and reported, as appropriate, on the CT SAE Report Form, in accordance with the [Requirements](#) section above.

### **8.1.4. Time Period for Collecting AE/SAE Information**

The time period for actively eliciting and collecting AEs and SAEs (“active collection period”) for each subject begins from the time the subject provides informed consent, which is obtained before the subject’s participation in the study (ie, before undergoing any study-related procedure and/or receiving investigational product), through and including a minimum of 28 calendar days after the last administration of the investigational product.

For subjects who are screen failures, the active collection period ends when screen failure status is determined.

